
7.3 Criteria to Discontinue Treatment with Nivolumab with or without Ipilimumab

Treatment with nivolumab with or without ipilimumab should be permanently discontinued for any of the following:

- Any Grade 2 drug-related uveitis or eye pain or blurred vision that does not respond to topical therapy and does not improve to Grade 1 severity within the re-treatment period OR requires systemic treatment
- Any Grade 3 non-skin, drug-related adverse event lasting $>$ 7 days, with the following exceptions for drug-related laboratory abnormalities, uveitis, pneumonitis, bronchospasm, diarrhea, colitis, neurologic toxicity, hypersensitivity reactions, and infusion reactions:

- Grade 3 drug-related uveitis, pneumonitis, bronchospasm, diarrhea, colitis, neurologic toxicity, hypersensitivity reaction, or infusion reaction of any duration requires discontinuation
- Grade 3 drug-related laboratory abnormalities do not require treatment discontinuation except:
 - Grade 3 drug-related thrombocytopenia > 7 days or associated with bleeding requires discontinuation
 - Any drug-related liver function test (LFT) abnormality that meets the following criteria require discontinuation:
 - * AST or ALT > 8 x ULN
 - * Total bilirubin > 5 x ULN
 - * Concurrent AST or ALT > 3 x ULN and total bilirubin > 2 x ULN
- Any Grade 4 drug-related adverse event or laboratory abnormality, except for the following events which do not require discontinuation:
 - Grade 4 amylase or lipase abnormalities that are not associated with symptoms or clinical manifestations of pancreatitis. It is recommended to consult with the PI for Grade 4 amylase or lipase abnormalities.
 - Isolated Grade 4 electrolyte imbalances/abnormalities that are not associated with clinical sequelae and are corrected with supplementation/appropriate management within 72 hours of their onset
- Any dosing interruption lasting > 6 weeks unless the sponsor-investigator is consulted and agrees with the rationale for resuming therapy after a delay > 6 weeks. Note that tumor assessments should continue as per protocol even if dosing is interrupted.
- Any adverse event, laboratory abnormality, or intercurrent illness which, in the judgment of the site investigator, presents a substantial clinical risk to the subject with continued nivolumab with or without ipilimumab dosing.

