12: MANDATORY: Blood samples for cfDNA and CTCs will be collected every 2 cycles (\pm 7 days) prior to treatment, corresponding to all imaging assessment time points and at time of EOT visit. Additionally, blood samples for cfDNA and CTCs will be collected at confirmatory imaging assessment time points. If EOT collection is within 2 weeks of prior collection, research samples do not need to be collected. For patients enrolled on the Single Cell Sequencing Cohort, whole blood for CTC collection and whole blood for plasma/PBMC isolation will not be collected.

ARM B: CALENDAR FOR SUBJECTS WITH SD/PD AFTER PRIMARY TREATMENT	SD/PD after Primary Treatment ⁴ ± 3 days			SD/PR/CR after nivolumab PLUS ipilimumab ⁵ ± 3 days	Every 2 cycles (± 7 days) ^{2,3}	End of Treatment Visit ^{6,7} ± 7 days	Long Term Follow Up ⁸ ± 14 days
Study Evaluation Cycle = 28 days	Nivolumab PLUS Ipilimumab			Nivolumab ALONE Cycles 3 +	While on treatment	Off Study Treatment; On Study Follow-up	
	C1D1	C1D22	C2D15	Day 1 of Cycle 3 onward +/- 3 days	Every 2 cycles (+/- 7 days)	Day 30	Every 6 months
REQUIRED ASSESSMENTS							
Physical Exam	X	X	X	X		X	
Vital signs and ECOG Performance Status ¹	X	X	X	X		X	
AEs & concomitant medications	X	X	X	X		X	X
LABORATORY ASSESSMENTS							
Complete Blood Cell Count with diff (CBC) ²	X	X	X	X		X	
Comprehensive Metabolic Profile (CMP) ²	X	X	X	X		X	
Thyroid Function (TSH and free T4) ²					X	X	
DISEASE ASSESSMENT							
CT of chest ³					X ³		
CT or MRI of abdomen and pelvis ³					X ³		
TREATMENT EXPOSURE							
Nivolumab	X	X		X			
Ipilimumab	X	X					
SPECIMEN COLLECTION							
Tumor Biopsy ⁹						X	
Research Blood Sample- Biomarkers ¹⁰					X	X	
Research Blood Sample- cfDNA and CTCs ¹¹					X	X	
FOLLOW-UP							
Survival Status, Subsequent Therapy							X

Key to Footnotes

1: Vital signs to include upright blood pressure, heart rate, respiratory rate, temperature, oxygen saturation, body weight (kg) and height (cm). Height at SCREENING ONLY.

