2: Hematology testing to include full CBC with WBC, ANC, hemoglobin, and platelet count and differential. Serum chemistry to include full comprehensive metabolic panel with sodium, potassium, chloride, bicarbonate, BUN, creatinine, glucose, calcium, albumin, AST, ALT, alkaline phosphatase, and total bilirubin. C1D1 laboratory assessments do not need to re-meet eligibility criteria. TSH and free T4 will be done every two cycles (8 weeks \pm 7 days), except when ipilimumab is added, TSH and free T4 will be obtained after 3 cycles (12 weeks \pm 7 days) instead of 2 cycles (8 weeks) to align with scan visits

3: Diagnostic CT chest and CT or MRI of the abdomen and pelvis should be obtained every 2 cycles (- 7 days). **NOTE:** When ipilimumab is added, imaging will be obtained after 3 cycles (~12 weeks \pm 7 days) instead of 2 cycles. If dosing is delayed, imaging should follow guidelines of cycles over absolute weeks.

4: **ADDITION OF IPILIMUMAB:** Subjects that show SD/PD with confirmatory scans after Primary Treatment (Arm B) will have ipilimumab added for 2 doses ONLY. During this time, nivolumab will be given every 3 weeks to match ipilimumab administration. Disease assessment scans will occur after completion of 3 cycles from the addition of ipilimumab to nivolumab. Nivolumab ALONE will be continued starting 5 weeks \pm 3 days after last dose of nivolumab PLUS ipilimumab at the start of cycle 3/day 1 from when ipilimumab is added to nivolumab.

5: **CR/PR/SD AFTER ADDITION OF IPILIMUMAB:** Subjects will continue nivolumab ALONE until PD. During this time nivolumab will be given every 4 weeks and disease assessment scans will occur every 2 cycles (8 weeks \pm 7 days).

6: **PD AFTER ADDITION OF IPILIMUMAB:** Subjects that experience PD after nivolumab PLUS ipilimumab will be taken off study treatment and continue follow up per protocol. Confirmatory scans for subjects with PD are not mandatory but may be attained 4 weeks later if clinically feasible. Subjects will be permitted to continue treatment beyond site investigator assessed progression as long as they meet the following criteria: (1) Site investigator-assessed clinical benefit AND (2) Subject is tolerating study drug.

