13.7 Efficacy Analysis

13.7.1 Primary Efficacy Analysis

Tumor assessment will be performed every 8 weeks. At the time of each restaging, subjects will be classified as achieving complete response (CR), partial response (PR), stable disease (SD), progressive disease (PD), or non-evaluable for response according to RECIST (Version 1.1) criteria.

Arm A: The proportion of subjects with sustained/continued PR or CR during the 1 year since the nivolumab discontinuation will be presented with a two-sided 90% CI using exact binominal method. Based on a sample size of 23 subjects, the confidence interval will be no wider than 0.37. For a targeted 35% PR or CR rate, the estimated PR or CR rate precision (width of two sided 90%CI) would be 0.35.

Arm B: The proportion of subjects with PR or CR during the 1-year from the date of first dose of ipilimumab will be presented with a two-sided 90% confidence interval calculated using the method of Atkinson and Brown, corresponding to the two-stage design.

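### The arm calendars let tumour scans slip with delayed dosing while other sections fix them in weeks; on-treatment shifts can date progression late and cost Arm B one scan in its one-year window

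*Combined protocol and SAP*

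**What the plan says.** **Cycle-based timing.** Footnote 3 of both the Arm A and Arm B calendars in Section 8 reads: "If dosing is delayed, imaging should follow guidelines of cycles over absolute weeks". The calendars define the unit: "Study Evaluation Cycle = 28 days". After ipilimumab is added, "imaging will be obtained after 3 cycles (~12 weeks", and later "disease assessment scans will occur every 2 cycles (8 weeks". Section 6 also states imaging in cycles, with weeks in brackets, and the opening of Section 10 calls for re-evaluation every two cycles.

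**Week-based timing.** Section 13.7.1 says: "Tumor assessment will be performed every 8 weeks". Section 2.7 sets Arm B scans 8 weeks apart, with the first 12 weeks after ipilimumab is added. Section 6.3.2, for patients whose ipilimumab waits for radiotherapy, puts restaging 12 weeks (±7 days) after ipilimumab starts. Section 7.3 adds: "Note that tumor assessments should continue as per protocol even if dosing is interrupted".

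**Delays.** Section 7.2 has a missed combination dose restart when it is safe, not at the next scheduled date. A held single-agent nivolumab dose resumes at the next scheduled date. The same section also allows a cycle to be either omitted or moved. The ordinary limit on a delay is 6 weeks, and Section 7.3 allows longer with the sponsor-investigator's agreement.

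**Endpoints affected.** Section 13.7.1 reports for Arm B: "The proportion of subjects with PR or CR during the 1-year from the date of first dose of ipilimumab". Section 13.2.1 defines the same endpoint with no one-year limit. Section 13.2.2 ends PFS at documented progression or death.

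**The concern.** Most drug-related non-skin events of Grade 2 or higher call for a delay (Section 7.1). If the scan moves with the dose, the timing of assessment depends on how well the patient tolerates treatment.

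Two consequences follow, in opposite directions. Progression is dated when a scan shows it, so a late scan tends to lengthen PFS. Response in Arm B is counted within a fixed year, so a shifted schedule gives fewer chances to record one. The sections also differ on which timing applies, so sites may handle the same delay differently.

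**Working it through.** **1. The first scan after ipilimumab (Arm B calendar and footnote 4; Section 7.2).**
The second combination dose is due at week 3. Cycle 3 starts 5 weeks after that dose, and the scan follows the end of cycle 3, 4 weeks later.
- On time: 3 + 5 + 4 = week 12.
- Second dose delayed by the ordinary maximum of 6 weeks, to week 9: 9 + 5 + 4 = week 18.

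**2. Later intervals.** Two 28-day cycles make 8 weeks. A cycle moved by 6 weeks makes the interval 8 + 6 = 14 weeks.

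**3. Dating of progression, 6-week shift.** A progression that the on-time scan would have shown is dated 6 weeks late. One that arises between the due scan and the actual scan is found 8 − 6 = 2 weeks sooner than the next on-time scan would have found it. Assuming progression is uniform over the stretched interval, the net delay is:
- 8-week interval stretched to 14: (8 × 6 − 6 × 2) / 14 = 2.6 weeks late.
- First interval stretched from 12 to 18: (12 × 6 − 6 × 2) / 18 = 3.3 weeks late.

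Over each later 8-week interval the two effects cancel: (2 × 6 − 6 × 2) / 8 = 0. The net delay therefore arises only in the interval that contains the hold.

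Section 13.7.2 may also report 12-month PFS. With a 2-week shift, the last scan before one year is at week 46 instead of week 52.

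**4. Arm B scans within one year (taken as 365 days).** Scan days are 84 + 56k from the first ipilimumab dose: 84, 140, 196, 252, 308 and 364, which is six scans (weeks 12 to 52). With a cumulative shift of d days:
- The sixth scan falls at 364 + d, past day 365 once d is 2 or more.
- Taken 7 days early, it falls at 357 + d, past day 365 once d is 9 or more.
- d = 42: scans at weeks 18, 26, 34, 42 and 50, and the next at week 58. Five remain.
- A second scan is lost only when 308 + d > 365, that is, d above 57.

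Table 2 in Section 10.3.4 asks for response confirmation at about 4 weeks or more. If that must also fall within the year, the scans at which a first response can count drop from five (to week 44) to four (to week 42 with a 6-week shift).

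**5. The plan's own Arm B figures (Section 13.3).** The design enters 20 subjects, stops at 1 or fewer responses, then goes to 57 and needs 6 or more. Exact power is the sum over x ≥ 2 of P(x of 20) × P(at least 6 − x of 37).

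| Quantity | Plan | Recomputed |
|---|---|---|
| Power at 20% | 92% | 92.13% |
| Type I error at 5% | 4.7% | 4.76% |
| Early stop at 5% | 73% | 73.58% |

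The figures agree; the last two match if truncated.

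**6. Effect of the lost scan on power.** The documents give neither a hold rate nor the share of responders first seen at week 52, so both are assumed. Let h be the share of responders with a hold that shifts the cycle (20–60%), and q the share of those who would first respond at the lost scan (2–20%). The detectable rate is 0.20 × (1 − hq), applied equally to both stages.

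| h | q | Detectable rate | Power |
|---|---|---|---|
| 0 | – | 20.0% | 92.1% |
| 20% | 2% | 19.9% | 92.0% |
| 40% | 5% | 19.6% | 91.4% |
| 60% | 20% | 17.6% | 86.6% |

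**The case against.** **The sections may not conflict outright.** Sections 6 and 10 also speak of cycles, and Section 13.7.1 is a summary that does not even mention the 12-week scan. The remark in Section 7.3 can be read as pointing back to the calendars, which would make footnote 3 the specific rule for delays. This stands as a possible reading. It does not account for the week-based timing in Sections 2.7 and 6.3.2, and once a shift exceeds 7 days a site has no stated way to choose.

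**Not every hold moves the scan.** A reader might infer that each toxicity hold delays imaging. The documents do not support that. A single-agent dose resumed at its next scheduled date need not shift the cycle, and the text does not say whether an omitted cycle counts.

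**Arm A is largely spared.** A reader might also infer that the Arm A primary endpoint is at risk. During observation there is no dosing to delay, so that endpoint and the first PFS event in observation are unaffected. Arm A is exposed only after nivolumab is restarted.

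**The stakes are limited.** PFS is secondary and descriptive, with no planned comparison between arms or by hold status. A lost scan cannot create a response, so the Arm B decision errs on the cautious side. Under the definition in Section 13.2.1, which has no one-year limit, no window is lost. All of this stands and limits the size of the point.

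**Conclusion.** The point holds for on-treatment delays that shift the cycle: a delayed combination dose, or a nivolumab cycle that is moved. For these, footnote 3 makes assessment timing depend on tolerance and sits against the week-based sections.

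- **PFS:** progression can be dated up to about 6 weeks late per ordinary hold. The net is about 2.6 to 3.3 weeks in the affected interval for a 6-week shift, if progression is uniform there. The bias lengthens apparent PFS.
- **Arm B response:** five scans instead of six for a shift of 9 days or more, under the one-year window of Section 13.7.1. The effect runs only downward. Power is 91.4% at middling assumptions and 86.6% at the extreme, against 92.1%.

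A reader might take this as a serious threat to the Arm B primary test. The documents do not show that: they give no hold rate, and the loss is small over most of the assumed range. The case for change rests on inconsistent instructions and tolerance-dependent scanning, which are cheap to remove.

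**What to change.** Delete the sentence on delayed dosing from footnote 3 of both arm calendars and state instead:

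*Tumour assessments are scheduled in calendar weeks regardless of dose delays or skipped cycles. Arm A: every 8 weeks (±7 days) from nivolumab discontinuation, and again from restart. Either arm, once ipilimumab is added: week 12 (±7 days) from the first ipilimumab dose, then every 8 weeks (±7 days).*

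Align the imaging text in Section 6, the opening of Section 10, the calendar headings, and the scan-linked thyroid tests and research blood draws. The Arm B footnote now prints the window as "should be obtained every 2 cycles (- 7 days"; set it to match the rest. Reconcile the one-year limit between Sections 13.2.1 and 13.7.1.

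**Cost.** No new procedure is needed, but more text changes than two footnotes. A scan and its linked blood draws may not coincide with a dosing visit. If the second combination dose slips to week 9, a week-12 scan falls 3 weeks after it instead of 9. How such a scan bears on stopping treatment is left to the existing provisions on confirmation and treatment beyond progression, which this change does not alter.

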8.1 Duration of Follow Up

Subjects who have an ongoing study treatment-related AE upon end of treatment visit will be followed until the event has resolved to baseline grade, the event is assessed by the site investigator as stable, new anticancer treatment is initiated, the subject is lost to follow-up, the subject withdraws consent, or until it has been determined that study treatment or participation is not the cause of the AE. After progression/treatment discontinuation, subjects will be followed for survival and receipt of next line therapies every 6 months until death or 2 years after treatment discontinuation. Follow-up will be via phone calls and through review of medical records.

9. BIOSPECIMEN STUDIES AND PROCEDURES

Correlative studies will be exploratory in nature. In this study, we will evaluate the immunomodulatory properties of nivolumab in combination with ipilimumab and correlate findings with outcomes. In addition, we will evaluate tumor tissue and TIMC for expression of PD-L1 in mandatory baseline biopsies and optional progression biopsies and correlate with outcomes. Lastly, we will evaluate mechanisms of resistance to therapy in optional progression biopsy specimens. Please see the Laboratory Manual for collection, processing, labeling and shipping instructions.

Whole blood for germline DNA and cfDNA plasma samples will be analyzed by investigators at collaborating institutions, such as the Broad Institute, for all patients enrolled on this trial. From these samples, the data will be submitted to the National Institutes of Health's Database for Genotypes and Phenotypes (dbGaP) and other public databases. Samples and data will be de-identified.

9.1 Blood for Germline DNA

- This sample will be drawn once prior to C1D1 treatment
- Five (5) mL of blood will be drawn into purple top vacutainers with EDTA. DO NOT use heparin as anticoagulant, since the polymer will tightly bind downstream PCR enzyme during sequencing.

9.2 Blood for Research Analysis

9.2.1 Biomarker Analysis

Blood will be collected for flow cytometry studies to analyze peripheral blood mononuclear cells. Additionally, plasma will be collected to analyze soluble biomarkers to include cytokines/chemokines and angiogenic/growth factors. This analysis will require 30 mL of blood in green or purple top tubes at each time point. These samples are to be collected prior to treatment C1D1, every 2 cycles corresponding with radiology imaging. If off treatment collection is within 2 weeks of prior collection, research samples do not need to be collected.

9.2.2 cfDNA Plasma

Plasma will be collected for genomic analysis of circulating free DNA (cfDNA). cfDNA assessments will require 10 mL of blood in an EDTA tube at each time point. These samples are to be collected prior to treatment C1D1, every 2 cycles corresponding with radiology imaging. If off treatment collection is within 2 weeks of prior collection, research samples do not need to be collected.

The cfDNA from each time point will be subjected to low pass whole genome sequencing to assess DNA quality, tumor purity (i.e. the approximate percentage of DNA isolated from peripheral blood originating from tumor rather than normal cells), and copy number profile of tumor DNA. For subjects with cfDNA of adequate quality and purity, we will also perform whole exome sequencing from cfDNA isolated at baseline, at best tumor response, and at progression.

9.2.3 CTC Analysis

CTC analysis will require 20mL of blood in EDTA tubes at each time point. These samples are to be collected during screening, prior to treatment C1D1, every 2 cycles, corresponding with radiology imaging. If off treatment collection is within 2 weeks of prior collection, research samples do not need to be collected.

9.3 Tissue Studies

Tissue will be collected to assess the immunomodulatory properties of nivolumab in combination with ipilimumab as determined immunohistochemistry assessment of immunologic parameters including, but not limited to, T cell subset markers (CD4, CD8, FoxP3, LAG3), cytokines/chemokines (IFN, TNF), immune regulation (PD-L2, CTLA-4), and tumor infiltrating lymphocytes (TILs). Additionally, mutation profiling of molecular mechanisms of response and resistance will be analyzed via whole exome sequencing and RNA sequencing.

Mutational profiling of molecular mechanisms of response and resistance will be analyzed via whole exome or whole genome sequencing and via RNA-sequencing. If fresh tissue is available, the specimen will be collected, as stated in this protocol and according to institutional guidelines, and put on ice to be transported to the processing laboratory. A portion of fresh tissue will be dissociated into a single cell suspension and frozen for future studies, including single cell transcriptome studies and cell line creation.

9.3.1 Archival tumor specimens

Archival tissue is MANDATORY if available. The archival specimen must contain adequate viable tumor tissue and be overall representative of the whole tumor (i.e. containing predominant and highest Fuhrman grade areas). Formalin-fixed paraffin-embedded tumor tissue blocks are preferred and should contain tumor areas that measure at least 1 cm square in aggregate.

Alternatively, a minimum of 30 unstained 4-micron-thick sections (on charged slides) can be provided. The unstained slides should be coated with paraffin. Surgical specimens are preferred with order of preference being 1) nephrectomy specimens and 2) metastectomy specimens. If surgical specimens are not available, core-needle biopsy specimens are acceptable. Fine-needle aspiration, brushings, cell pellet from pleural effusion, bone marrow aspirate/biopsy are not acceptable.

9.3.2 Fresh Tumor Specimens

MANDATORY tumor biopsies will be performed on all subjects prior to treatment, and OPTIONAL tumor biopsies will be performed on subjects at the time of disease progression and for patients in arm A at time of disease progression after discontinuation of nivolumab.

For patients enrolled on the Single Cell Sequencing Cohort the biopsy schedule will be as follows:

Arm A:

Mandatory biopsy at baseline

Optional biopsy at time of response following discontinuation of nivolumab

Mandatory biopsy at final treatment discontinuation/off study

Arm B:

Mandatory biopsy at baseline

Mandatory biopsy at final treatment discontinuation/off study

Progression biopsies are strongly recommended in patients who demonstrate a response to therapy and subsequently progress. Biopsies will be obtained in a manner that minimizes risk and will be taken only if there is no intervening condition (e.g., thrombocytopenia or neutropenia) that, in the opinion of the site investigator, increases the likelihood of procedural complications to an unacceptable level.

Biopsies should be performed per institutional standards and/or operator preference. Blood samples will be drawn within 2 weeks of the biopsy to document an acceptable coagulation profile (INR \leq 1.5, PTT \leq 60, platelets $>$ 50,000). Aspirin and NSAIDS should be discontinued 5 days prior to the biopsy.

Preferred biopsy sites include: lymph nodes, peripheral based liver lesions, exophytic soft tissue components associated with bone lesions, subcutaneous nodules, pleural-based lesions, and kidney lesions.

In the case that a patient will be undergoing a cytoreductive nephrectomy, metastatectomy, or biopsy within 12 months of enrolling on the study with no intervening systemic therapy from the time of surgery to study enrollment, fresh tissue obtained from the surgical specimen may be used to replace the mandatory baseline fresh tumor biopsy.

